## 8 Safety and Adverse Events

### 8.1 Definitions

#### Unanticipated Problems Involving Risk to Subjects or Others

Any incident, experience, or outcome that meets all of the following criteria:

- Unexpected in nature, severity, or frequency (i.e. not described in study-related documents such as the IRB-approved protocol or consent form, the investigators brochure, etc.)
- Related or possibly related to participation in the research (i.e. possibly related means there is a reasonable possibility that the incident experience, or outcome may have been caused by the procedures involved in the research)
- Suggests that the research places subjects or others at greater risk of harm (including physical, psychological, economic, or social harm).

#### Adverse Event

An **adverse event** (AE) is any symptom, sign, illness or experience that develops or worsens in severity during the course of the study. Abnormal results of diagnostic procedures are considered to be adverse events if the abnormality:

- results in study withdrawal
- is associated with a serious adverse event
- is associated with clinical signs or symptoms
- leads to additional treatment or to further diagnostic tests
- is considered by the investigator to be of clinical significance

In the following differentiation between medical history and AEs (see below), the term “condition” may include abnormal physical examination findings, symptoms, or diseases.

- Conditions that started before signing of informed consent and for which no symptoms or treatment are present until signing of informed consent are recorded as medical history (e.g. seasonal allergy without acute complaints).
- Conditions that started before signing of informed consent and for which symptoms or treatment are present after signing of informed consent, at *unchanged intensity*, are recorded as medical history.
- Conditions that pertain to efficacy variables of this study, i.e. findings on PET and which are considered pre-existing medical conditions, are not considered AEs unless there is worsening. This also implies that the indication for the imaging procedure and the confirmation of a diagnosis will not be considered as an AE.

#### Serious Adverse Event

Adverse events are classified as serious or non-serious. A **serious adverse event** is any AE that is:

- fatal
- life-threatening
- requires or prolongs hospital stay

- results in persistent or significant disability or incapacity
- a congenital anomaly or birth defect
- an important medical event

All adverse events that do not meet any of the criteria for serious should be regarded as ***non-serious adverse events***.

### **Adverse Event Reporting Period**

The study period during which adverse events will be reported is defined as 24 hours post injection of the radiotracer.

### **Preexisting Condition**

A preexisting condition is one that is present at the start of the study. A preexisting condition should be recorded as an adverse event if the frequency, intensity, or the character of the condition worsens during the study period.

### **General Physical Examination Findings**

At screening, any clinically significant abnormality should be recorded as a preexisting condition. At the end of the study, any new clinically significant findings/abnormalities that meet the definition of an adverse event must also be recorded and documented as an adverse event.

### **Post-study Adverse Event**

All unresolved adverse events should be followed by the investigator until the events are resolved, the subject is lost to follow-up, or the adverse event is otherwise explained. At the last scheduled visit, the investigator should instruct each subject to report any subsequent event(s) that the subject, or the subject's personal physician, believes might reasonably be related to participation in this study. The investigator should notify the study sponsor of any death or adverse event occurring at any time after a subject has discontinued or terminated study participation that may reasonably be related to this study. The sponsor should also be notified if the investigator should become aware of the development of cancer or of a congenital anomaly in a subsequently conceived offspring of a subject that has participated in this study.

### **Hospitalization, Prolonged Hospitalization or Surgery**

Any adverse event that results in hospitalization or prolonged hospitalization should be documented and reported as a serious adverse event unless specifically instructed otherwise in this protocol. Any condition responsible for surgery should be documented as an adverse event if the condition meets the criteria for an adverse event.

Neither the condition, hospitalization, prolonged hospitalization, nor surgery are reported as an adverse event in the following circumstances:

- Hospitalization or prolonged hospitalization for diagnostic or elective surgical procedures for a preexisting condition. Surgery should ***not*** be reported as an outcome of an adverse event if the purpose of the surgery was elective or diagnostic and the outcome was uneventful.
- Hospitalization or prolonged hospitalization required to allow efficacy measurement for the study.
- Hospitalization or prolonged hospitalization for therapy of the target disease of the study, unless it is a worsening or increase in frequency of hospital admissions as judged by the clinical investigator.

## **8.2 Recording of Adverse Events**

At each contact with the subject, the investigator must seek information on adverse events by specific questioning and, as appropriate, by examination. Information on all adverse events should be recorded immediately in the source document, and also in the appropriate adverse event module of the case report form (CRF). All clearly related signs, symptoms, and abnormal diagnostic procedures results should be recorded in the source document, though should be grouped under one diagnosis.

All adverse events occurring during the imaging AE reporting period must be recorded. The clinical course of each event should be followed until resolution, stabilization, or until it has been determined that the study treatment or participation is not the cause. Serious adverse events that are still ongoing at the end of the study period must be followed up to determine the final outcome. Any serious adverse event that occurs after the study period and is considered to be possibly related to the study treatment or study participation should be recorded and reported immediately.

## **8.3 Reporting of Serious Adverse Events and Unanticipated Problems**

Investigators must conform to the adverse event reporting timelines, formats and requirements of the various entities to which they are responsible, but at a minimum those events that must be reported are those that are:

- related to study participation,
- unexpected, and
- serious or involve risks to subjects or others  
(see definitions, section 8.1).

If the report is supplied as a narrative, the minimum necessary information to be provided at the time of the initial report includes:

- |  |  |
|--|--|
| 

• Study identifier

• Subject number

• A description of the event

• Date of onset

 | 

• Current status

• Whether study was discontinued

• The reason why the event is classified as serious.

 |
|--|--|

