Statistical Methodology	
Primary Efficacy Analysis: Nominal continuous variables will be represented as the mean +/- SD and categorical variables will be noted as the number and percentage of total. Pearson chi-square test will be utilized to determine statistical significance for continuous variables whereas a Student's two-sample t-test will be implemented to determine statistical significance for continuous variables. Univariate and multivariate analyses will be performed when relevant. Statistical significance will be set a priori as a p-value less than 0.05. Concordance and discordance of Ga-DOTATATE PET/CT with FDG and NH3 PET/CT for the presence or absence of CS will be calculated and utilizing FDG and NH3 PET/CT as the “gold-standard” for CS, the sensitivity and specificity of Ga-DOTATATE for the detection of CS will be determined. All statistical analyses will be performed using JMP Pro 9 (SAS Institute INC. Cary, North Carolina).
 
Safety: The overall safety profile will be assessed in terms of imaging agent related adverse events, and vital signs.

-------------------------	---

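### Section 8 states its reporting conditions for serious adverse events inconsistently across the 24-hour boundary, and the safety summary is limited to events attributed to the imaging agent

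*Combined protocol and SAP*

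**What the plan says.** Several parts of the protocol bear on this.

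- **Adverse Event Reporting Period (under 8.1):** "The study period during which adverse events will be reported is defined as 24 hours post injection of the radiotracer". No recipient or deadline is given.
- **8.2, inside the window:** "All adverse events occurring during the imaging AE reporting period must be recorded". The sentence concerns recording.
- **8.2, after the window:** the trigger is "Any serious adverse event that occurs after the study period and is considered to be possibly related to the study treatment or study participation". The instruction for an event of that kind is that it "should be recorded and reported immediately". Expectedness is not a condition.
- **8.3:** investigators must meet the requirements of the bodies they answer to, and "at a minimum those events that must be reported are those that are" related, unexpected, and serious or a source of risk. The list refers the reader to the definitions in 8.1 and carries no time limit.
- **8.1, unanticipated problems:** the relatedness criterion is "Related or possibly related to participation in the research". Unexpected means not described in study documents such as the protocol, consent form or brochure.
- **Hospitalization, Prolonged Hospitalization or Surgery (under 8.1):** "Any adverse event that results in hospitalization or prolonged hospitalization should be documented and reported as a serious adverse event", subject to listed exceptions. Neither relatedness nor expectedness is required.
- **Post-study Adverse Event (under 8.1):** the sponsor should be told of a death or adverse event after participation ends if it may reasonably be related.
- **8.3.1:** unanticipated problems go to the IRB in a written report, with no deadline.
- **Study Summary, Statistical Methodology:** "The overall safety profile will be assessed in terms of imaging agent related adverse events, and vital signs". Section 7 contains no safety analysis that widens this.

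**The concern.** One would expect the hours just after injection to carry reporting conditions at least as broad and as prompt as those for later events. Here the only sentence that asks for immediate reporting applies after the window. It also drops the expectedness condition that the general floor in 8.3 imposes. Two people applying section 8 to the same in-window event could reach different answers on whether it must be reported, to whom and how fast.

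The safety summary raises a related but separate problem. Patients with suspected cardiac sarcoidosis can have cardiac events from the disease itself. If only events attributed to the agent enter the summary, and there is no control group, a clean safety statement may partly reflect attribution rather than what was observed.

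**Working it through.** **Reporting conditions.** The documents give no figure to reproduce, so the check is a comparison of the rules. Each row is a class of serious event, and 8.3 is read together with 8.1, so that possibly related events count.

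| Class of serious event | Onset within 24 h | Onset after 24 h |
|---|---|---|
| (a) At least possibly related, unexpected, no hospitalization | Reporting-period statement applies; meets the 8.3 floor; no deadline | 8.2: immediate report; also meets the 8.3 floor |
| (b) At least possibly related, expected, no hospitalization | Reporting-period statement applies; recorded under 8.2; outside the 8.3 floor; no recipient or deadline | 8.2: immediate report |
| (c) Causes or prolongs hospitalization, no exception applies | Reported as serious whatever its cause or expectedness; no deadline | Same duty; immediate under 8.2 if possibly related |
| (d) Unrelated, no hospitalization | Reporting-period statement applies; recorded under 8.2; outside the 8.3 floor | No reporting sentence applies |

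Reading across:

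1. In (b) the post-window rule is explicit and immediate, while the in-window event rests on a general statement without recipient or deadline and lies outside the 8.3 floor. For example, such an event at 3 hours falls outside the floor, and the same event at 30 hours calls for an immediate report.
2. In (a) and (c) the event is reportable on both sides. Only the word on timing differs.
3. In (d) coverage is broader inside the window than after it.

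The inconsistency therefore lies in the expectedness condition for (b) and in the absence of any in-window timing for (a) to (c).

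**Safety summary.** The input is 15 patients (Study Summary). Suppose one patient has an in-window event that is judged not related to the agent.

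- All events summarised: 1/15 = 6.7%. Exact (Clopper-Pearson) 95% lower limit = 1 − 0.975^(1/15) = 0.2%. The upper limit p solves (1 − p)^15 + 15p(1 − p)^14 = 0.025, giving 31.9%.
- Agent-related events only: 0/15 = 0%. Upper limit = 1 − 0.025^(1/15) = 21.8%.

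One attribution decision moves the observed proportion by 6.7 percentage points and the upper limit by 31.9 − 21.8 = 10.1 points. The documents give no expected event frequency and no indication of how often events would be judged unrelated, so this shows sensitivity and is not a forecast. It says nothing about the reporting conditions, because all in-window events are recorded whichever reporting rule applies.

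**The case against.** A reader might infer that a possibly related serious event hours after injection need not be reported at all. The documents do not support that reading, for these reasons:

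- The reporting-period definition says in-window adverse events will be reported.
- 8.3 is a floor, has no time limit, and leaves other bodies' requirements in force. The contrast between inside and after the window comes from 8.2, not from 8.3.
- Its reference to 8.1 brings in possibly related events, so the missing word in the 8.3 list is not a firm gap.
- Hospitalizing events are reportable whatever their cause or expectedness, apart from the listed exceptions.
- The post-window sentence says should, not must.

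Expectedness in 8.1 also means being described in study documents, not being common in the patient population. The protocol text available lists no expected adverse events, and the consent pages are not available for review, so class (b) may be small.

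On the summary, section 7 puts all subject data in listings, and 8.4 requires regular assessment of the number and type of serious events with no attribution filter. An event judged unrelated would not disappear from the record.

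All of this stands and limits the point. It does not remove the expectedness mismatch in class (b), supply in-window timing, or widen the stated safety summary. The other bodies' requirements are not set out in the protocol, so they cannot be relied on to close the gap.

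**Conclusion.** The point holds in limited form, at low severity. Section 8 does not state relatedness, expectedness, timing and recipient consistently. A serious, related or possibly related event that counts as expected and does not lead to hospitalization is explicitly subject to immediate reporting only after 24 hours. How many events this could affect cannot be determined from the documents. No statistical figure in the plan changes.

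The restriction of the safety summary to agent-related events is a separate and firmer point. In an uncontrolled study of 15 patients, each patient whose event is left out changes the reported proportion by 6.7 percentage points. This assumes that the study investigators make the attribution. The protocol assigns safety monitoring to them in 8.4 and names no one else for the task.

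**What to change.** 1. **Safety summary (Study Summary, repeated in section 7).** Summarise all adverse events with onset in the 24-hour window, and show related or possibly related events as a subset. The data are already to be recorded, so this costs one extra table row or column. The downside is that a few disease-related events will appear in the summary.
2. **Section 8.** Reconcile the reporting-period definition, the hospitalization and post-study paragraphs, 8.2, 8.3 and 8.3.1. State once, for both periods, the relatedness standard (related or possibly related), whether expectedness matters, the timing, and who receives the report. The conditions should be no narrower inside the window than after it. Let the unanticipated-problem criteria in 8.1 decide only what goes to the IRB. The cost is a wording amendment and possibly a few additional reports.

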### **8.3.1 Investigator reporting: notifying the Mayo Clinic IRB**

#### **Reporting Process**

Unanticipated problems posing risks to subjects or others as noted above will be reported to the Mayo Clinic IRB as a written report of the event (including a description of the event with information regarding its fulfillment of the above criteria, follow-up/resolution and need for revision to consent form and/or other study documentation).

## **8.4 Safety Monitoring**

Subject safety will be monitored continuously by the Investigators. This safety monitoring will include careful assessment and appropriate reporting of adverse events and a regular assessment of the number and type of serious adverse events.

## 9 Data Handling and Record Keeping

### 9.1 Confidentiality

Information about study subjects will be kept confidential and managed according to the requirements of the Health Insurance Portability and Accountability Act of 1996 (HIPAA). Those regulations require a signed subject authorization informing the subject of the following:

- What protected health information (PHI) will be collected from subjects in this study
- Who will have access to that information and why
- Who will use or disclose that information
- The rights of a research subject to revoke their authorization for use of their PHI.

In the event that a subject revokes authorization to collect or use PHI, the investigator, by regulation, retains the ability to use all information collected prior to the revocation of subject authorization.

### 9.2 Source Documents

Source data is all information, original records of clinical findings, observations, or other activities in a clinical trial necessary for the reconstruction and evaluation of the trial. Source data are contained in source documents. Examples of these original documents, and data records include: hospital records, clinical and office charts, laboratory notes, memoranda, subjects' diaries or evaluation checklists, pharmacy dispensing records, recorded data from automated instruments, copies or transcriptions certified after verification as being accurate and complete, microfiches, photographic negatives, microfilm or magnetic media, x-rays, subject files, and records kept at the pharmacy, at the laboratories, and at medico-technical departments involved in the clinical trial.

Source documents for the imaging protocol will be kept in a secure location by the principal investigator ([name]) or his designee.

### 9.3 Data Management Plan

We will create a database to store patient data. This database will be programmed in REDCap (Research Electronic Data Capture). REDCap is a secure, web-based application with the capacity for direct export to Excel and common statistical packages (SPSS, SAS, Strata, R). REDCap has electronic CRF (eCRF)s, real-time data entry validation, audit trails, user authentication, data logging and encryption. It is HIPAA compliant with mechanisms in place to ensure confidentiality. In addition, logical data checks will be used to assess data quality for mis-entry. Suspect data entries will be flagged for re-review and confirmation by the investigative team. When data are complete and all suspect entries addressed for a time period, the database will be "locked" for analysis. Analysis will use only this final locked version.

### 9.4 Data Sharing Plan

Clinical data will be exported from REDCap into proper statistical software format for analysis. The final dataset will be provided in proper format to investigators participating in data analysis. The mode of data sharing will be by downloading from REDCap from secure accounts. Data will be secured by electronic safeguards.

## 10 Ethical Considerations

This study is to be conducted accordance with applicable US government regulations and international standards of Good Clinical Practice, and applicable institutional research policies and procedures.

This protocol and any amendments will be submitted to Mayo Clinic Internal Review Board (IRB), in agreement with local legal prescriptions, for formal approval of the study conduct.

All subjects for this study will be provided a consent form describing this study and providing sufficient information for subjects to make an informed decision about their participation in this study. This consent form will be submitted with the protocol for review and approval by the IRB for the study. The formal consent of a subject, using the IRB-approved consent form, must be obtained before that subject undergoes any study procedure. The consent form must be signed by the subject or legally acceptable surrogate, and the investigator-designated research professional obtaining the consent.

## 11 Study Finances

### 11.1 Funding Source

CV Prospective Grant (FP00095637)

### 11.2 Conflict of Interest

The primary investigator and other study investigators have no relevant conflicts of interest.

